Surgical Procedures	Minor	
 Hold one or more IPs at investigator's discretion on day of surgery IPs may be restarted at same dose level upon recovery 	
 Ibrutinib CC-122
	Major	
 Hold one or more IPs for 3 to 7 days prior to surgery through 3 to 7 days post surgery Restart IPs upon recovery and at least 3 to 7 days post surgery at the same dose level 	
Infusion Reaction	Grade 1-2	
 Reduce infusion rate ($\leq 50\%$ prior rate) or interrupt infusion and treat symptoms Upon resolution, continue or resume infusion; infusion rate increments and intervals may resume at the increments and intervals as appropriate for the treatment dose if no further infusion reaction symptoms 	
 Obinutuzumab
	Grade 3 (severe) infusion reaction	
 Interrupt infusion and manage symptoms Upon resolution, restart infusion at $\leq 50\%$ prior rate; infusion rate escalations can resume at the increments and intervals as appropriate for the treatment dose if no further infusion reaction symptoms Permanently discontinue if Grade 3 or higher infusion-related symptom occurs with re-challenge 	
	Grade 4 (life threatening) infusion reaction	
 Stop infusion immediately; permanently discontinue 	

Table 14: Dose Reduction Guidelines (Continued)

Adverse Event	Grade	Action	Agent to be considered for interruption/reduction (in descending order)
Progressive Multifocal Leukoencephalopathy	All	
 Permanently discontinue 	
 Obinutuzumab
Pneumonitis	Grade 2	
 Hold one or more IPs at investigator's discretion Once symptoms have resolved completely, CC-122 and/or ibrutinib may be restarted at the next lower dose level. 	
 CC-122 Ibrutinib
	≥ Grade 3	
 Discontinue one or more suspected IPs permanently 	

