8.2.9.2.4. Pneumonitis

Pneumonitis has been observed in patients taking CC-122. The diagnosis should be considered in subjects presenting with non-specific respiratory signs and symptoms such as hypoxia, pleural effusion, cough, dyspnea, or interstitial pulmonary infiltrates, and in whom infectious, neoplastic and other causes are excluded by appropriate investigations. Subjects should be specifically advised to report promptly any new or worsening respiratory symptoms they experience.

Those with radiological features suggestive of non-infectious pneumonitis but with minimal (Grade 1) symptoms may continue CC-122 without dose alteration. For drug-related Grade 2 pneumonitis, CC-122 treatment should be interrupted and corticosteroids may be indicated. Once symptoms have resolved completely, CC-122 may be reintroduced at the next lower dose level. For drug-related Grade 3 or 4 pneumonitis CC-122 must be permanently discontinued and corticosteroids are recommended until clinical symptoms have resolved.

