8.2.11.1. Interstitial Lung Disease (ILD)

Cases of ILD have been reported in patients treated with ibrutinib. Monitor patients for pulmonary symptoms indicative of ILD. Should symptoms develop, follow the protocol dose modification guidelines as outlined in **Table 16**.

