8.2.12.2. Ibrutinib Dose Reduction Steps

Ibrutinib dose reduction steps are shown in [Table 16](#).

Table 16: Ibrutinib Dose Reduction Steps

Non-Hematologic Adverse Events	
Toxicity Occurrence	Action to be Taken
First	Withhold ibrutinib until recovery to Grade \leq 1 or baseline; may restart at original dose level, 420 mg daily
Second	Withhold ibrutinib until recovery to Grade \leq 1 or baseline; may restart at 1 dose level lower, 280 mg daily
Third	Withhold ibrutinib until recovery to Grade \leq 1 or baseline; may restart at 1 dose level lower, 140 mg daily
Fourth	Discontinue Ibrutinib

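### For lung toxicity in which ibrutinib is suspected, Table 16 (via Section 8.2.11.1) and the Table 14 pneumonitis row give conflicting instructions, and the protocol does not settle which prevails

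*Protocol*

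**What the plan says.** **Section 8.2.11.1 (ILD, ibrutinib).** If symptoms appear, sites are to "follow the protocol dose modification guidelines as outlined in" Table 16. No grade is given, and neither Table 14 nor Section 8.2.9.2.4 is mentioned. Section 8.2.2.2 likewise refers toxicity-related changes to ibrutinib to Section 8.2.12.2, where Table 16 sits.

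**Table 16 (Section 8.2.12.2, non-hematologic events).** The action depends on how many times the toxicity has occurred. Each of the first three times, ibrutinib is withheld until recovery to Grade 1 or lower, or baseline. After the first it "may restart at original dose level, 420 mg daily"; after the second it "may restart at 1 dose level lower, 280 mg daily"; after the third the level is 140 mg. The fourth occurrence ends ibrutinib.

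**Table 14, pneumonitis row (Section 8.2.9.2).** The agents listed are CC-122 and ibrutinib. At Grade 2: "Hold one or more IPs at investigator's discretion", then "Once symptoms have resolved completely, CC-122 and/or ibrutinib may be restarted at the next lower dose level". At Grade 3 or higher: "Discontinue one or more suspected IPs permanently". The text introducing the table says its criteria should be used for dose modifications.

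**Section 8.2.9.2.4 (pneumonitis, CC-122 only).** "For drug-related Grade 2 pneumonitis, CC-122 treatment should be interrupted". Reintroduction is at the next lower level after complete resolution, and drug-related Grade 3 or 4 events end CC-122 permanently.

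**The concern.** An Arm B subject who develops inflammatory lung changes can be classed as ILD or as pneumonitis. The protocol draws no line between them: Section 8.2.9.2.4 names interstitial infiltrates among the presentations of pneumonitis, and SAP Section 11.1.1 follows the area under a single interstitial pneumonitis query. A site that starts from Section 8.2.11.1 is never directed to the permanent-stop rule. A site that starts from Table 14 meets it at once.

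Two things are at stake. The first is subject safety: the protocol warns of lung toxicity for both drugs, and Amendment 7 lets enrolled subjects stay on treatment for up to 24 cycles of CC-122, with 3 further cycles of ibrutinib supplied. The second is reporting: SAP Section 11.1.1 tabulates adverse events leading to discontinuation, reduction or interruption of each drug, so the same event may land in different tables depending on which passage the site followed.

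**Working it through.** There is no stated figure to reproduce. The check sets the passages side by side by drug and grade.

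| Situation | Section 8.2.11.1 and Table 16 | Table 14, pneumonitis row | Section 8.2.9.2.4 |
|---|---|---|---|
| Ibrutinib suspected, first event, Grade 2 | Restart at 420 mg on recovery to Grade 1 or lower, or baseline | Restart one level lower, only on complete resolution | Silent on ibrutinib |
| Ibrutinib suspected, first event, Grade 3 or higher | Restart at 420 mg on the same recovery condition | Permanent stop | Silent on ibrutinib |
| CC-122, Grade 2, hold | Silent on CC-122 | Hold worded as discretionary | Should be interrupted |
| CC-122, Grade 2, restart | Silent on CC-122 | Complete resolution, next lower level | Same |
| CC-122 suspected, Grade 3 or higher | Silent on CC-122 | Permanent stop | Same |

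1. *Ibrutinib, Grade 2.* The recovery condition and the restart dose both differ. One level below 420 mg is 280 mg, which Table 16 reaches only after the second event.

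2. *Ibrutinib, Grade 3 or higher.* One passage permits restart and the other forbids it. This holds only when ibrutinib is a suspected agent, because Table 14 stops suspected drugs only.

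3. *CC-122.* Table 14 and Section 8.2.9.2.4 agree on restart and on Grade 3 or higher. They differ only in how the Grade 2 hold is worded.

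4. *Precedence.* Section 8.2.9.2 points to Table 14 in general terms. Section 8.2.2.2 points to Section 8.2.12.2 for ibrutinib, and Section 8.2.11.1 points to Table 16 for ILD specifically. The readable text does not rank them.

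5. *Effect on the safety counts.* Section 8.2.9 makes any dose reduction in the DLT window a DLT. A Grade 2 lung event with ibrutinib resumed one level lower in the window (Table 14) is therefore a DLT; resumed at 420 mg (Table 16), it is not a DLT by that route. One such event could move a cohort from 0/3 to 1/3, or from 1/6 to 2/6, which is the not-tolerated threshold. The Section 4.1 late-toxicity limit of more than 20% also counts reductions and discontinuations. In a cohort of six, 1/6 = 16.7% is below the limit and 2/6 = 33.3% is above it. These shifts arise only if CC-122 is not itself reduced or stopped for the same event, since that would count anyway.

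**The case against.** The best defence is that the two tables have different jobs: Table 14 gives the action for each event, and Table 16 supplies the ibrutinib dose ladder. Table 14 uses that ladder for liver and gastrointestinal events and departs from it for pneumonitis, which looks deliberate. Section 8.2.9.2 says to use Table 14, Section 8.2.9.1 lets Table 14 override its general hold rule, and Table 16 is permissive in tone. This is a reasonable reading, and it means a claim that nothing in the protocol speaks to precedence would go too far. It does not close the point, because Section 8.2.11.1 is the specific ILD instruction and names Table 16 alone. Text between Table 14 and Section 8.2.9.2.3 is blacked out, so a ranking there cannot be excluded.

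A reader might infer more than the documents support:

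- *That three rules conflict with one another.* Section 8.2.9.2.4 governs CC-122 and Table 16 governs ibrutinib, so those two cannot contradict each other. The Grade 2 hold difference is weak: the discretion in Table 14 may concern which drug to hold, and its restart clause presupposes a hold.
- *That Table 16 expressly covers every grade.* It sets no upper grade limit, but its recovery target implies an event above Grade 1.
- *That the Grade 3 conflict changes the DLT count.* Under Section 8.2.7, a Grade 3 or higher non-hematologic event in the window, not clearly due to progression, a procedure or intercurrent illness, is already a DLT whatever is done with the dose.
- *That Table 16 is the wrong target for the cross-reference.* That would choose between clinical rules, and the documents do not decide it.

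It is also fair that the SAP tables are descriptive, that enrollment is closed, and that Phase 2 will not proceed. The DLT consequence is therefore largely retrospective.

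**Conclusion.** The point holds as a conflict between two instructions for one drug. With ibrutinib suspected, Table 16 and the Table 14 pneumonitis row differ at Grade 2 on the recovery condition and the restart dose. At Grade 3 or higher they differ on whether restart is allowed at all, so a first event ranges from restart at 420 mg to a permanent stop. The Grade 2 hold of CC-122 is a secondary wording difference.

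This rests on three assumptions: that ibrutinib is a suspected agent, that the same presentation can be called ILD or pneumonitis, and that no redacted text sets precedence. The documents give no event rate, so the number of subjects affected cannot be stated. The case for acting is the safety of subjects still on treatment and consistent recording of dose actions, not any effect on a hypothesis test.

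**What to change.** Issue a protocol clarification letter that reconciles Sections 8.2.2.2, 8.2.9.2 (including the Table 14 pneumonitis row), 8.2.9.2.4, 8.2.11.1 and 8.2.12.2 (Table 16). It should state one rule for ILD/pneumonitis for each drug and grade, say whether the two terms are handled alike, and make every cross-reference agree with that rule. The sponsor's clinical team must choose the rule.

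The cost is the letter and its distribution to sites; no analysis needs redesign. When safety data are reviewed, lung events already recorded in ibrutinib-treated subjects can be listed with grade, suspected drug and dose action, so that readers can see which instruction was followed.

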8.2.12. Dose Reduction Steps

If a subject develops toxicity, the dose of CC-122 may be reduced as outlined in **Table 15** and ibrutinib as outlined in **Table 16**.

8.2.12.1. CC-122 Dose Reduction Steps

Recommendations for dose reduction steps for CC-122 are presented in **Table 15**. Up to 3 dose reductions will be permitted for patients who receive an initial starting dose of 3.0 mg, 3.5 mg or 4.0 mg, provided data from the fixed-dose cohorts during the escalation phase demonstrates that

1.5 mg, 2.0 mg and 2.5 mg are active (i.e. at least 1 objective response (CR or PR/PRL) was observed).

Table 15: CC-122 Dose Reduction Steps

Current Dose	0.5 mg	1.0 mg	1.5 mg	2.0 mg	2.5 mg	3.0 mg	3.5 mg	4.0 mg
Dose Reduction 1	0.25 mg	0.5 mg	1.0 mg	1.5 mg	2.0 mg	2.5 mg	3.0 mg	3.5 mg
Dose Reduction 2	0.1 mg	0.25 mg	0.5 mg	1.0 mg	1.5 mg	2.0 mg	2.5 mg	3.0 mg
Dose Reduction 3	D/C	D/C	D/C	D/C	D/C	1.5 mg	2.0 mg	2.5 mg

Abbreviation: D/C = Discontinue.

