8.2.2. Dose Escalation Phase

8.2.2.1. Arm A: CC-122 Single Agent

Subjects assigned to Arm A will be administered a starting dose of 1.0 mg CC-122 orally on a 5/7-day (5 continuous days out of 7 days per week) schedule starting at Cycle 1 Day 1 with intrasubject dose escalation every 2 weeks at 0.5 mg increments at the discretion of the investigator as tolerated up to a maximum dose of 4.0 mg for a total of 24 cycles of CC-122, or until disease progression, unacceptable toxicity or discontinuation for any other reason, whichever is earlier. All treatment cycles are 28 days. Each dose will be taken in the morning with about 8 ounces of water. CC-122 may be taken up to 12 hours late if dosing has been delayed on a single day; otherwise that day's dose should be omitted.

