8.2.9.1. General Dose Modification Guidelines

Subjects will be evaluated for AEs at each visit with the NCI CTCAE (version 4.03) used as a guide for the grading of severity, with the exception of tumor flare (NCI CTCAE version 3.0), [REDACTED] and laboratory abnormalities as recommended by the IWCLL guidelines for the diagnosis and treatment of chronic lymphocytic leukemia [REDACTED] as listed below:

Subjects experiencing related AEs or SAEs \geq Grade 3 must interrupt dosing of the responsible IP or both IPs until resolution of the toxicity to \leq Grade 1 or baseline severity unless as otherwise indicated in [Table 14](#). If IP-related events do not resolve to \leq Grade 1 or baseline severity within 28 days despite adequate medical management, the sponsor's study medical monitor should be notified.

The dose of CC-122 may be reduced successively by one level from the starting dose. There will be no more than one dose level reduction from one cycle to the next unless otherwise permitted after consultation with the sponsor medical monitor. In addition, if a subject continues to experience unacceptable toxicity after two dose reductions (with the exception of CC-122 per [Table 15](#) where up to 3 dose reductions may be allowed for selected doses), IP will be discontinued permanently. If a dose is reduced for toxicity other than a Grade 4 non-hematological toxicity, re-escalation is permitted after the toxicity is resolved. If the toxicity recurs after re-escalation, the subject should remain at the lower dose level. Subjects who experience a Grade 4 non-hematological toxicity may not have their dose re-escalated.

For the combination of CC-122 and ibrutinib or obinutuzumab, in the event of a toxicity requiring dose modification, CC-122 should be considered for interruption and dose reduction first if possible. If the subject continues to require dose modification after a dose hold and/or reduction of CC-122 a dose interruption of obinutuzumab or ibrutinib or reduction of ibrutinib may be considered.

Dose interruptions lasting beyond 28 days should be discussed with the sponsor's study medical monitor.

If it becomes necessary to permanently stop administration of one of the IPs, continuation on the other IP will require discussion and agreement between the sponsor's study medical monitor and the investigator.

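### The third CC-122 dose reduction depends on the starting dose in the text of Protocol 8.2.12.1 but on the current dose in Table 15, and 8.2.9.1 does not settle which applies

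*Protocol*

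**What the plan says.** Three places in the protocol bear on a third reduction of CC-122.

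- **Section 8.2.12.1, text.** As many as three reductions are allowed "for patients who receive an initial starting dose of 3.0 mg, 3.5 mg or 4.0 mg". A proviso follows: data from the fixed-dose cohorts must show that "1.5 mg, 2.0 mg and 2.5 mg are active (i.e. at least 1 objective response (CR or PR/PRL) was observed").
- **Section 8.2.12.1, Table 15.** The columns are headed by the current dose, from 0.5 to 4.0 mg. The row "Dose Reduction 3" shows discontinuation for 0.5 to 2.5 mg, and 1.5, 2.0 and 2.5 mg for current doses of 3.0, 3.5 and 4.0 mg. The table has no activity condition.
- **Section 8.2.9.1.** Treatment ends permanently "if a subject continues to experience unacceptable toxicity after two dose reductions". CC-122 is exempted by reference to Table 15, where "up to 3 dose reductions may be allowed for selected doses". The same paragraph describes CC-122 reductions as successive one-level steps counted from the starting dose.

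Starting and current dose differ by design. In Arm A, "Subjects assigned to Arm A will be administered a starting dose of 1.0 mg CC-122 orally" (Section 8.2.2.1), and escalation may go up to 4.0 mg in 0.5 mg steps every 2 weeks. Subjects enrolled in Arm A under earlier amendments began at 0.25 or 0.5 mg and may also escalate (Section 4.1). In Arms B and C, subjects in lower fixed-dose cohorts may move up once the SRC approves, and the SRC may add intrasubject escalation cohorts (Section 4.1).

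**The concern.** One rule is stated with two different reference doses. For a subject whose current dose is higher than the starting dose, the text and the table can give different answers to whether CC-122 may continue after two reductions. The section containing the stop rule points to the table but does not say which dose selects the subject.

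At stake is permanent discontinuation for toxicity. Two sites could manage the same subject differently, each with a section of the protocol in support. The difference would then reach the SAP summaries that describe tolerability: reasons for discontinuing IP (SAP Section 6), dose reductions (SAP Section 8.4) and TEAEs leading to discontinuation or dose reduction of CC-122 (SAP Section 11.1.1). The text is still in use, because under Amendment 7 subjects with clinical benefit may stay on treatment for up to 24 cycles of CC-122.

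**Working it through.** The plan gives no figure to reproduce, so the check compares the two rules across dose combinations.

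**Inputs**

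- Starting doses: 0.25 mg (earlier Arm A amendments, Section 4.1) and the eight doses in Table 15, 0.5 to 4.0 mg.
- Current doses: the eight doses in Table 15, taken at or above the starting dose.
- Text rule: a third reduction is permitted if the starting dose is 3.0, 3.5 or 4.0 mg. The activity condition is assumed met.
- Table rule: a third reduction is available if the current dose is 3.0, 3.5 or 4.0 mg. Current dose is taken as the dose held when the series of reductions begins.
- Where the text rule gives no third reduction, the two-reduction stop in Section 8.2.9.1 is applied.

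**Number of combinations**

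Counting the current doses available for each starting dose from 0.25 mg upward: 8 + 8 + 7 + 6 + 5 + 4 + 3 + 2 + 1 = 44.

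| Starting dose | Current dose | Text with 8.2.9.1 | Table 15 | Combinations |
|---|---|---|---|---|
| 0.25–2.5 mg | 0.5–2.5 mg | no third step | discontinue | 5 + 5 + 4 + 3 + 2 + 1 = 20 |
| 0.25–2.5 mg | 3.0, 3.5, 4.0 mg | no third step | 1.5, 2.0, 2.5 mg | 6 × 3 = 18 |
| 3.0–4.0 mg | 3.0–4.0 mg | third step | third step | 3 + 2 + 1 = 6 |

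The total is 20 + 18 + 6 = 44. The rules disagree in the 18 combinations of the middle row and nowhere else. These are dose combinations, not subjects, and not all of them need occur in every arm.

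**Can a subject reach the conflict?**

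In Arm A the number of escalations from 1.0 mg is (current dose − 1.0)/0.5, at no less than 2 weeks each:

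- 3.0 mg: (3.0 − 1.0)/0.5 = 4 escalations, 8 weeks
- 3.5 mg: (3.5 − 1.0)/0.5 = 5 escalations, 10 weeks
- 4.0 mg: (4.0 − 1.0)/0.5 = 6 escalations, 12 weeks

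So the design allows it. No Arm A subject has a starting dose of 3.0 mg or more, so the permission in the text never covers an Arm A subject. Table 15 covers any who reach 3.0 mg.

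**The activity condition**

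If 1.5, 2.0 and 2.5 mg have not been shown active, the text withdraws the third reduction even for subjects who started at 3.0 mg or more, while Table 15 still shows it. The 6 combinations in the last row would then disagree as well.

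**Does Section 8.2.9.1 decide?**

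It refers to Table 15, which favours current dose. It also counts reductions from the starting dose, and its exemption covers selected doses without defining them. Following it to 8.2.12.1 leads to both reference doses.

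**The case against.** The best defence is that the sentence in 8.2.12.1 only grants permission. It says who may have a third reduction, not that nobody else may. The only stop rule is in 8.2.9.1, and it exempts CC-122 through Table 15. On this reading the table governs. The activity condition also refers to the fixed-dose cohorts, which in the current design belong to Arms B and C. The sentence may therefore have been meant for subjects enrolled directly at 3.0–4.0 mg, with Arm A left to the table. Table 15 is, moreover, introduced as recommendations.

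Part of this stands. A reader might infer that 8.2.12.1 by itself bars a third reduction in Arm A and obliges those subjects to stop. It does not say so: discontinuation follows only when it is read with the two-reduction limit in 8.2.9.1. But if the table governs alone, the starting-dose limit and the activity proviso in the text have no effect, and the protocol does not say that they have none. Neither 8.2.12.1 nor 8.2.9.1 restricts the sentence to particular arms. The SAP treats the initial CC-122 dose as a fixed attribute of the subject (Section 5.2.1), so starting dose cannot simply be taken to mean current dose.

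The objection is also right that the scope is narrow. Arm A escalation requires no DLT or dose reduction at the current level (Section 4.1) and recovery from related AEs (Section 8.2.8). An affected subject must pass those checks up to 3.0 mg or more and later need three reductions. Enrolment has ended and Phase 2 will not proceed, which limits the practical reach further.

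**Conclusion.** The protocol is inconsistent as written, and nothing in the protocol or SAP reconciles it. For subjects escalated to 3.0–4.0 mg from a start below 3.0 mg who need a third reduction, it supports both discontinuing and continuing CC-122. The presence of the activity condition in the text but not in the table is a second mismatch in the same place.

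The point is minor, and three larger readings do not hold.

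- **All of Arm A.** The figure of about 20 is the planned size of the arm. The documents do not say how many subjects reached 3.0 mg, or how many of those needed a third reduction.
- **Every escalated subject in Arms B and C.** At a current dose of 2.5 mg or less both readings end in discontinuation, and the documents do not show that anyone in these arms was escalated to 3.0 mg.
- **The dose-finding result.** The NTD and MTD rest on DLTs in the 28-day window, where any dose reduction already counts as a DLT (Section 8.2.9). The late-toxicity rule in Section 4.1 counts reductions and discontinuations together, so a subject facing a third toxicity-related reduction would usually have been counted already.

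What can change is the management of individual subjects and the descriptive summaries of discontinuation and dose reduction. The conclusion rests on reading the current-dose columns of Table 15 as the dose held when reductions begin, and the comparison of combinations assumes that the activity condition is met.

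**What to change.** Reconcile the text of Section 8.2.12.1, Table 15 and Section 8.2.9.1 so that all three use one stated reference dose, starting or current, for a third CC-122 reduction. State whether the activity condition applies to the steps in Table 15, and whether the rule is the same in Arm A as in Arms B and C. Which rule is clinically right is for the sponsor and the SRC to decide; this review takes no view.

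The cost is a protocol clarification letter. No change to the sample size or the analysis methods is needed. The listings already planned in SAP Section 11.1.1, of AEs leading to withdrawal and to dose reduction or interruption, can help to identify any subject to whom the two readings applied.
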